## 4.0 Eligible Patients

All patients receiving treatment with Adcetris

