## 9.1 Data to be recorded in Patient Enrollment Form

### 1) Outcome measures

Name of the institution, name of the investigator completing Patient Enrollment Form, expected date of the start of treatment with Adcetris, patient identification number, patient initial, sex, date of birth, diagnosis, performance status, CD30, past history of severe hypersensitivity to any ingredient of Adcetris, expected concomitant use of other antineoplastic drugs, and presence/absence of infections, peripheral nerve disorders, hepatic disorders, severe renal disorders, or pregnancy/breast-feeding

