### 9.2.3 Treatment given

#### 1) Outcome measures

Treatment with Adcetris and premedication to prevent infusion reaction (dose, date of premedication, and reasons for premedication to prevent infusion reaction and its discontinuation), (use or non-use, type, and date of) post-baseline hematopoietic stem cell transplantation, (presence/absence, name, and duration of) drugs other than Adcetris used for the treatment of the primary disease, and (presence/absence, name, and duration of) drugs used for the prevention of infection

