### b) Infections

It is expected that Adcetris is used in patients who are immunocompromised due to prior treatment or the prior disease or those who are complicated with infection, and the incidence of infections is likely to be high. Therefore, the profile of infections in Japanese patients as an adverse event of particular interest (i.e., the incidence and temporal relationship with the onset of neutropenia/lymphopenia) will be determined.

c) Neutropenia

It is expected that Adcetris is used in patients with decreased neutrophil count due to prior treatment, which may increase the risk of infection and result in a high incidence of infection/severe infection. It is important to control the neutrophil count to allow for continuation of treatment (including dose reduction and restart of treatment after treatment interruption) in terms of the prevention of infection. Therefore, the profile of neutropenia in Japanese patients as an adverse event of particular interest will be determined (i.e., the status of treatment with Adcetris and neutrophil count control will be assessed and information useful for continuation of treatment with Adcetris will be collected).

d) Infusion reactions

Infusion reactions are characteristic of monoclonal antibody preparations, the profile of infusion reactions in Japanese patients as an adverse event of particular interest (including the status of premedication and the percentage of patients using premedication to prevent infusion reactions [use/non-use of premedication to prevent infusion reactions]) will be determined.

e) Pulmonary disorders

The occurrence of pulmonary disorders in Japanese patients receiving monotherapy with Adcetris as an adverse event of particular interest will be determined.

3) When to collect outcome measure data

From the start of treatment with Adcetris until the completion of 16 cycles (or upon discontinuation of treatment with Adcetris)

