#### 10.4.2 Factors that may affect the safety of Adcetris

The frequency of adverse events observed during the observation period will be analyzed by patient background factors (sex, age, presence/absence of concurrent renal disorders, and presence/absence of concurrent hepatic disorders) and treatment given (the status of treatment with Adcetris and concomitant medications).

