4.0 Treatment Given

4.1 Treatment given

(1) Analysis sets to be used

Safety analysis set, safety analysis set (Hodgkin’s lymphoma), and safety analysis set (anaplastic large-cell lymphoma)

(2) Data to be analyzed

For each data item, patients will be stratified into the following categories below, and the frequency will be calculated. In addition, summary statistics of continuous variable will be calculated:

Data item	Category
Initial dose of Adcetris	<1.2 mg/kg, 1.2 mg/kg, >1.2 mg/kg to <1.8 mg/kg, 1.8 mg/kg, or >1.8 mg/kg
Mean dose of Adcetris	<1.2 mg/kg, 1.2 mg/kg, >1.2 mg/kg to <1.8 mg/kg, 1.8 mg/kg, or >1.8 mg/kg
Dose of Adcetris per 3 weeks	<1.2 mg/kg, 1.2 mg/kg, >1.2 mg/kg to <1.8 mg/kg, 1.8 mg/kg, or >1.8 mg/kg
Duration of treatment with Adcetris	1, 2, 3, 4, 5, 6, 7, 8, 9, 10, 11, 12, 13, 14, 15, 16, or ≥ 17 cycles
Reason(s) for discontinuation of Adcetris	Treatment goal achieved, adverse event(s), lost to follow-up, transfer to another hospital, pregnancy, inadequate response, and/or other
Post-baseline hematopoietic stem cell transplantation	Absent, present, or unknown
Type of post-baseline hematopoietic stem cell transplantation	Autologous or homologous
Days from the date of the last dose of Adcetris to hematopoietic stem cell transplantation (autologous) (Post-baseline hematopoietic stem cell transplantation: autologous)	-
Duration of treatment with Adcetris prior to	-

hematopoietic stem cell transplantation (autologous) (Post-baseline hematopoietic stem cell transplantation: autologous)	
Days from the date of the last dose of Adcetris to hematopoietic stem cell transplantation (homologous) (Post-baseline hematopoietic stem cell transplantation: homologous)	-
Duration of treatment with Adcetris prior to hematopoietic stem cell transplantation (homologous) (Post-baseline hematopoietic stem cell transplantation: homologous)	-
Drug(s) other than Adcetris used for the treatment of the primary disease	Absent or present
Drug(s) used for the prevention of infection	Absent or present
Specific drug(s) used for the prevention of infection	Antibiotics/synthetic antibacterial agents, antifungals, antivirals, trimethoprim-sulfamethoxazole combinations, and/or other prophylactics against infections

(3) Figure/table number

Tables 4.1-1 to 4.1-3

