5.9.13 Occurrence of adverse drug reactions of pulmonary disorder and infections

(1) Analysis sets to be used

Safety analysis set, safety analysis set (Hodgkin’s lymphoma), and safety analysis set (anaplastic large-cell lymphoma)

(2) Data to be analyzed

The incidence of pulmonary disorders considered related to Adcetris for each CTCAE grade (the worst one) will be calculated by pulmonary disorder and PT. PTs and PT Codes will be presented in ascending order.

In addition, the incidence of pulmonary disorders considered related to Adcetris for each CTCAE grade (the worst one) will be calculated by patient demographics and baseline characteristics.

The CTCAE grade (the worst one) is higher in the order of Grades 5, 4, 3, 2, 1, and unknown. If the same patient has multiple occurrences of pulmonary disorders or there are multiple occurrences of the same PT, the highest CTCAE grade (the worst one) for the patient or PT will be counted once for the category:

Data item	Category
CTCAE Grade (the worst one) for pulmonary disorders	Grade 1, Grade 2, Grade 3, Grade 4, Grade 5, or unknown

Items and categories of patient demographics and baseline characteristics

Data item	Category
History of or concurrent pulmonary disorder	Absent or present
Smoking history	Non-smoker or smoker * Patients other than those who have never smoked will be classified into “smoker.”
Prior radiotherapy	Absent or present

(3) Figure/table number

Tables 5.9.13-1 to 5.9.13-4

5.10 analysis setanalysis setanalysis setList of actions taken with Adcetris in patients experiencing peripheral nerve disorders considered related to Adcetris

(1) Analysis sets to be used

Patients included in the safety analysis set analysis setanalysis setwho experience peripheral nerve disorders considered related to Adcetris

(2) Data to be analyzed

(3) For each patient, a list of the following data items: patient number, diagnosis, action taken or not taken with Adcetris, reason for action taken, date of dosing and dose for each cycle, date of onset of peripheral nerve disorder, CTCAE grade (the worst one), outcome, and the date of outcome. If the

same patient has multiple occurrences of peripheral nerve disorder, all these occurrences will be counted. Figure/table number

Table 5.10

5.11 List of actions taken with Adcetris in patients experiencing neutropenia considered related to Adcetris

(1) Analysis sets to be used

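### The protocol promises pulmonary disorders under Adcetris monotherapy, but no planned output separates monotherapy from use with other antineoplastic drugs

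*Protocol*

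**What the plan says.** Protocol 9.2.5 2) takes five events of particular interest in turn. For pulmonary disorders, item e) states that "The occurrence of pulmonary disorders in Japanese patients receiving monotherapy with Adcetris" will be determined. None of the other four items mentions monotherapy, and the sentence is the same in every protocol version in the file.

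Eligibility (Protocol 4.0) is "All patients receiving treatment with Adcetris". The enrolment form (Protocol 9.1) asks about "expected concomitant use of other antineoplastic drugs". The case report form (Protocol 9.2.3) records "presence/absence, name, and duration of) drugs other than Adcetris used for the treatment of the primary disease".

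SAP 5.9.13 plans "The incidence of pulmonary disorders considered related to Adcetris for each CTCAE grade", by preferred term, in the safety analysis set and its Hodgkin's and anaplastic large-cell subsets. Its factor table has three rows: history of or concurrent pulmonary disorder, smoking, and prior radiotherapy. The item "Drug(s) other than Adcetris used for the treatment of the primary disease" appears in SAP 4.1 as a patient count and in SAP 5.3 as a split of the overall adverse drug reaction percentage.

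**The concern.** The protocol names a population for this event, and the analysis section for the event does not use it. Patients given other antineoplastic drugs may have a different pulmonary risk, and the 5.9.13 rate would mix the two groups. A reader who takes that rate as the answer to Protocol 9.2.5 2) e) would be reading a figure for all users. At stake is whether the survey can answer a safety question that it sets itself, from data that it already collects.

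**Working it through.** **1. Can combination patients enter the 5.9.13 denominator?** Yes. SAP 1.1.1 defines the safety set as treated patients without a major protocol violation who can be evaluated for safety. The table in SAP 2.0 excludes patients from safety evaluation only if they never received the drug or have no safety data. Neither mentions other antineoplastic drugs. The SAP does not use the word pooled; pooling follows because 5.9.13 neither restricts nor stratifies.

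**2. Does another output supply the monotherapy figure?**
- SAP 4.1 only counts users of other drugs.
- SAP 5.3 splits the percentage with any adverse drug reaction, not pulmonary disorders.
- SAP 5.1 and 5.2 list preferred terms, but not by use of other drugs.
- SAP 5.10 and 5.11 give patient listings for peripheral nerve disorders and neutropenia. There is none for pulmonary disorders, so the figure cannot be rebuilt from listings.
- The other two SAP versions in the file and both supplements define no monotherapy subset.

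**3. The protocol's own event counts.** Inputs from Protocol 3.2 are 140 patients, an infusion reaction rate of 11% and a pulmonary disorder rate of 6%. With exact binomial tails:
- P(X ≥ 10 | 140, 0.11) = 0.9518, and with 139 patients 0.9490, so 140 is reproduced as the smallest sufficient number.
- P(X ≥ 4 | 140, 0.06) = 0.9713 and P(X ≥ 5 | 140, 0.06) = 0.9273. The statement of at least 4 pulmonary cases is therefore correct if 95% is read as at least 95%.
- Expected pulmonary cases: 140 × 0.06 = 8.4. One case is about 12% of that (1/8.4).

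**4. What pooling could do.** Let c be the share of patients on other drugs and RR their relative pulmonary risk. Neither is in the documents; both are assumptions. Pooled rate = 0.06 × (1 − c) + 0.06 × RR × c.

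| c | RR | Pooled rate |
|---|---|---|
| 0 | any | 6.0% |
| 0.10 | 2 | 0.054 + 0.012 = 6.6% |
| 0.10 | 3 | 0.054 + 0.018 = 7.2% |
| 0.20 | 2 | 0.048 + 0.024 = 7.2% |
| 0.20 | 3 | 0.048 + 0.036 = 8.4% |

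With RR = 1 the rate stays at 6.0% for any c. The calculation applies RR to the full 6%, whereas 5.9.13 counts only events considered related, so it is illustrative.

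**5. What the split costs in events.** P(X ≥ 4) at 6% in the monotherapy stratum:

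| Share removed (assumed) | n | P(at least 4) |
|---|---|---|
| 0% | 140 | 0.971 |
| 10% | 126 | 0.948 |
| 20% | 112 | 0.909 |

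The smallest n that keeps 95% is 127 (0.9504).

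**The case against.** The strongest reply is that the monotherapy sentence stands under the rationale for choosing the events, not in the purpose or the analysis section. Protocol 1.0 frames the task around patients using the drug in Japan, Protocol 2.0 has no monotherapy limit, and Protocol 10.4 assigns the safety analyses to the safety set, which 5.9.13 uses. Protocol 5.0 describes only single-agent dosing, so monotherapy may just describe the expected use. Part of this stands: correcting the protocol wording would reconcile the documents equally well. It does not remove the mismatch, because the sentence says that this occurrence will be determined and is alone among the five events in naming that population.

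A second reply is that other drugs are handled elsewhere. Protocol 10.4.2 asks for adverse event frequency by "treatment given (the status of treatment with Adcetris and concomitant medications", and SAP 5.3 makes that split for overall reactions. This is true, but it yields no pulmonary figure.

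A third is that the relatedness filter removes contaminated cases. It removes some: Protocol Table 3 classes an event as not related when another cause is very likely. The same table still allows an event to be related when concomitant drugs contribute, and SAP 1.0 counts every event not judged unrelated. Events with a possible second cause therefore stay in.

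Finally, the effect may be small or nil. Even the upper illustrative rate of 8.4% lies inside the exact 95% interval for 8 of 140 (2.5% to 10.9%). That limits the importance of the point, not its correctness.

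**Conclusion.** The mismatch is real and follows from the wording alone: as planned, no table reports pulmonary disorders under monotherapy. It is worth correcting because correction is cheap, not because a large error has been shown. The size is unknown. It is zero if no patient receives other drugs or if their pulmonary risk is the same. The range of 6.6-8.4% against 6.0% rests wholly on an assumed 10-20% share and 2-3 times the risk.

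A reader might infer two stronger claims. One is that the protocol means to compare the observed rate with the 6% planning rate and that pooling spoils this comparison. No such comparison is planned: Protocol 3.2 uses 6% only to state how many cases 140 patients should yield, and SAP 5.9.13 specifies neither a test nor a reference rate. The other is that the 5.9.13 rate is known to be inflated. The documents give neither the combination share nor the risk in those patients, so they cannot support that.

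**What to change.** Add the other-drugs item already used in SAP 4.1 and 5.3 (absent/present) to the factor table of SAP 5.9.13. Three details need to be written down:

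- **One classification rule for everyone.** Assign each patient, with or without a pulmonary event, by the same criterion, for example any recorded use that overlaps the Adcetris observation period. A criterion based on use before onset would not work, because patients without an event have no onset date.
- **Drugs started partway.** State how they are handled, using the durations on the case report form, and apply this equally to patients with and without events.
- **Reporting.** Give the absent stratum with its own denominator and a two-sided 95% CI, beside the overall result.

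The alternative is to amend Protocol 9.2.5 2) e) so that it refers to all treated patients, as the SAP does.

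The cost is one row from data already collected, plus the classification rule. The price in precision is the smaller denominator: if more than 13 of 140 patients fall outside the stratum (140 − 127), the probability of at least 4 cases at 6% drops below 95%. This should be stated with the result, and it is a reason to keep the overall figure alongside.

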**Table 1 Definition of an Adverse Event**

An adverse event (AE) is any untoward or undesirable medical occurrence in a patient linked in time with the use of a pharmaceutical/ medicinal product and which does not necessarily have to have a causal relationship with this treatment or may or may not be considered related to the product. An adverse event can therefore be any unfavorable and unintended sign (including an abnormal laboratory finding), symptom, or disease temporally associated with the use of a medicinal product, whether or not related to the medicinal product.

Adverse events also include:

- Symptoms observed in an infant breast-fed by a mother receiving treatment with Adcetris.

**Table 2 Criteria for the Seriousness of Adverse Events**

An adverse event meeting any of the following criteria will be considered serious:

1. Results in death.
2. Is life-threatening.
3. Requires inpatient hospitalization or prolongation of existing hospitalization.
4. Results in persistent or significant disability/incapacity.
5. Is a congenital anomaly/birth defect.
6. Is a medically important condition due to any of the above 1 to 5, including those listed in “Takeda Medically Significant AE List.”

Takeda Medically Significant AE List

•Acute respiratory failure/acute respiratory distress syndrome (ARDS)	•Anaphylactic shock
•Torsade de pointes/ventricular fibrillation/ventricular tachycardia	•Acute kidney failure
•Malignant hypertension	•Pulmonary hypertension
•Convulsive seizure (including convulsion and epilepsy)	•Pulmonary fibrosis (including interstitial pneumonia)
•Agranulocytosis	•Neuroleptic malignant syndrome/malignant hyperthermia
•Aplastic anemia	•Spontaneous abortion/stillbirth and fetal death
•Toxic epidermal necrolysis/oculomucocutaneous syndrome (Stevens-Johnson syndrome)	•(Suspected) transmission of infection via a drug
•Hepatic necrosis	•(Suspected) endotoxic shock
•Acute hepatic failure	

**Table 3 Criteria for the Assessment of Causal Relationship between Adverse Events and Adcetris**

Causality	Assessment criterion
Related	There is a temporal relationship between the event and Adcetris (and the clinical course after treatment discontinuation). Or, there are other contributing factors, such as the primary disease, concurrent illnesses, and concomitant medications/therapies, but it is also likely that the event is attributable to Adcetris.
Not related	There is no temporal relationship between the event and Adcetris. Or, it is very likely that the event is attributable to other factors, such as the primary disease, concurrent illnesses, and concomitant medications/therapies.
Indeterminate	There is limited information required for the assessment of causal relationship, such as temporal relationship between the event and Adcetris (and the clinical course after treatment discontinuation), the primary disease, concurrent illnesses, and concomitant medications/therapies.

## 10.0 Data to Be Analyzed and Methods of Analysis

### 10.1 Patient disposition

Data to be analyzed includes the number of enrolled patients, the number of patients whose case report forms are available, and the number of patients included in and excluded from the safety/efficacy analysis set and reasons for inclusion/exclusion.

### 10.2 Patient demographics and baseline characteristics

Data to be analyzed includes sex, age, disease duration, site of involvement, and clinical stage.

### 10.3 Treatment given

Data to be analyzed includes the status of treatment with Adcetris and concomitant medications.

### 10.4 Safety

The measures specified below will be analyzed using the safety analysis set. Adverse events will be coded using MedDRA/J and summarized using (Preferred Terms [PTs]) and System Organ Classes [SOCs]).

#### 10.4.1 Occurrence of adverse events

The frequency of adverse events observed during the observation period will be analyzed by type, time of onset, seriousness, and Adcetris.

#### 10.4.2 Factors that may affect the safety of Adcetris

The frequency of adverse events observed during the observation period will be analyzed by patient background factors (sex, age, presence/absence of concurrent renal disorders, and presence/absence of concurrent hepatic disorders) and treatment given (the status of treatment with Adcetris and concomitant medications).

#### 10.4.3 Changes in laboratory test data over time

Summary statistics of laboratory test values at baseline and post-baseline will be calculated.

### 10.5 Efficacy

The measures specified below will be analyzed using the efficacy analysis set.

#### 10.5.1 Best response

The best response after 16 cycles of treatment with Adcetris (or upon discontinuation of treatment with Adcetris) will be analyzed.

#### 10.5.2 Overall survival

The time to death (regardless of the cause of death) will be analyzed using the “final observation date” in specified in Section 9.2.4.3 as the date of survival confirmation and the date of outcome of an adverse event with “Died/fetal” recorded in the Outcome field specified in Section 9.2.5 as the date of death

### 10.6 Interim analyses

For patients whose case report forms are collected through November 30, 2014 with evaluable safety evaluation, analyses similar to the ones described in Sections 10.1 to 10.4 will be performed to evaluate and analyze safety information obtained in this study at an early stage and publish them as appropriate.

## 11.0 Posting of Information Regarding This Study

Prior to the start of the study, Takeda Pharmaceutical Company Limited will register information regarding this study to the public website specified below.

- Japan Pharmaceutical Information Center-Clinical Trials Information
- ClinicalTrials.gov (a clinical trial registration system provided by the National Institutes of Health)

### 14.0 Other Important Information

#### 14.1 Protocol amendment

During the study, the sponsor will monitor the occurrence of adverse drug reactions and serious adverse drug reactions that cannot be predicted by the progress of the study and precautions for use, the presence/absence of an increase in the frequency of specific adverse drug reactions, and the appropriateness of outcome measures, and review and amend this protocol as appropriate. If the approval of partial changes to “Dosage and Administration” or “Indication” is obtained during the study, the sponsor will consider the necessity of amendment of this protocol as appropriate, and amend the protocol as appropriate.

#### 14.2 Measures to be taken in response to issues/questions

If any safety and/or efficacy issue is detected, the sponsor will examine data closely and consider what measures should be taken.

Appendix 1 Study Schedule

Time point Procedure		Observation period				
		At the time of patient enrollment	At the start of treatment with Adcetris	During treatment	After 16 cycles	Upon discontinuation of treatment
Patient enrollment	Date of the expected initial dose of Adcetris					
	Patient identification number					
	Patient initial					
	Sex					
	Date of birth					
	Diagnosis					
	Performance status					
	CD30					
	Past history of severe hypersensitivity to any ingredient of Adcetris					
	Expected concomitant use of other antineoplastic drugs					
	Presence/absence of infections					
	Presence/absence of peripheral nerve disorders					
	Presence/absence of hepatic disorders					
	Presence/absence of severe renal disorders					
	Presence/absence of pregnancy/breast-feeding					
Patient demographics and baseline characteristics	Date of diagnosis of Hodgkin or anaplastic large-cell lymphoma					
	Site of involvement					
	ALK (in patients with anaplastic large cell lymphoma)					
	Clinical stage					
	Presence/absence of B symptoms					
	ECOG Performance Status					
	Therapeutic category					
	Hypersensitivity disposition					
	Viral test results					
	Past history of and concurrent pulmonary disorders					
	Past history of and concurrent malignant tumours					
	Concurrent illness (other than pulmonary disorders and malignant tumours)					
	Past history (other than pulmonary disorders and malignant tumours)					
	Height and weight					
	Smoking history					
Prior treatment for Hodgkin's or anaplastic large cell lymphoma						

Time point Procedure		Observation period				
		At the time of patient enrollment	At the start of treatment with Adcetris	During treatment	After 16 cycles	Upon discontinuation of treatment
Treatment given	Treatment with Adcetris		○	○		
	Post-baseline hematopoietic stem cell transplantation		← ○ →			○
	Drug(s) other than Adcetris used for the treatment of the primary disease		← ○ →			○
	Drug(s) used for the prevention of infection		← ○ →			○
Tests and assessments	Laboratory tests (red blood cell count, hemoglobin level, white blood cell count, neutrophil count, lymphocyte count, platelet count, and liver and kidney function tests)		← ○ →			○
	Best response				○	○
	Date of the final observation				○	○
	Presence/absence of pregnancy (for females only)		← ○ →			○
	Adverse events		← ○ →			○

○ : Data collected

← ○ → Data collected throughout the period

Appendix 2 Best Response Assessment Criteria (Revised Response Criteria for Malignant Lymphoma\*)

\* Extracted from “General Rules for the Clinical and Pathological Studies on Tumors of Hematopoietic and Lymphoid Tissues, March 2000 [First Edition]”

For patients with PET scan data available

Assessment	Criteria
CR	
All the following criteria are met:
 
1)-1 Routinely FDG-avid lymphoma The patient is PET negative. If the patient is PET negative, any residual tumor on CT does not matter.
 
1)-2 Variably FDG-avid lymphoma The patient did not undergo PET before treatment. If the patient was negative before treatment, the patient must meet all the following criteria:
 
[1] All nodal target lesions are normal. [2] All extranodal target lesions have resolved. [3] All nodal non-target lesions are normal. [4] The image shows the resolution of all nodal lesions in all organs including the spleen and the liver. [5] All extranodal non-target lesions have resolved.
 
2) A patient with bone marrow infiltration at baseline must be negative for bone marrow infiltration. A patient with no bone marrow infiltration at baseline should be regarded as “negative” because bone marrow test is not required.
 
3) The patient has no new lesion.

PR	
All the following criteria are met:
 
1)-1 Routinely FDG-avid lymphoma If the patient had one or more PET positive lesions, or was PET negative AND had bone marrow infiltration at baseline, the patient must be positive for bone marrow infiltration at the time of restaging (or have not undergone testing).
 
1)-2 Variably FDG-avid lymphoma If the patient did not undergo a PET scan or was PET negative prior to treatment, no PET assessment should be performed.
 
2) The patient has a 50% or more decrease (reduction) in the SPD of target lesion from baseline.
 
3) All nodal non-target lesions are normal or free from enlargement.
 
4) All extranodal non-target lesions have resolved or free from enlargement.
 
5) Bone marrow infiltration does not matter. Testing is not required.
 
6) The patient has no new lesion.

SD	
The patient achieved a response of <PR and >PD.

PD	
If the patient is not assessed as achieving CR but meets any of the criteria 1 and 2 to 6 and 7 listed below, the patient will be assessed as having progressive disease (PD). If the patient meets any of the criteria listed below after being assessed as achieving CR, the patient will be assessed as having a relapsed disease (RD):
 
1)-1 Routinely FDG-avid lymphoma The patient has one or more PET positive lesions.
 
1)-2 Variably FDG-avid lymphoma If the patient did not undergo a PET scan or was PET negative prior to treatment, no PET assessment should be performed.
 
2) The patient has a 50% or more increase in the SPD of target lesion from the minimum SPD.
 
3) The patient has an obvious increase in the nodal non-target lesion (a 50% or more increase in the long

	
diameter) or re-enlargement.
 
4) The patient has an obvious increase in the extranodal non-target lesion (a 50% or more increase in the long diameter) or recurrence.
 
5) The long diameter of the nodal target lesion which was once normalized and assessed as CR exceeded 1.5 cm. The extranodal target lesion which once resolved reappeared.
 
6) The patient has a new lesion.
 
7) The patient became positive after being once negative for bone marrow infiltration.

--	--

For patients with no PET scan data available

Assessment	Criteria
CR	
All the following criteria are met:
 
 
1) All nodal target lesions are normal.
 
2) All extranodal target lesions have resolved.
 
3) All nodal non-target lesions are normal.
 
4) The image shows the resolution of all nodal lesions in all organs including the spleen and the liver.
 
5) All extranodal non-target lesions have resolved.
 
6) There is no enlarged liver, spleen, or kidney (all lesions have resolved).
 
7) There is no tumor-related symptom (fever and night sweat) (all symptom have resolved) OR no abnormal tumor-related laboratory test results (tumor-related increase in LDH) (normal).
 
8) A patient with bone marrow infiltration or indeterminate at baseline must be negative for bone marrow infiltration. A patient with no bone marrow infiltration at baseline should be regarded as “negative” because bone marrow test is not required.
 
9) The patient has no new lesion.
 

CRu	
The patient had bone marrow infiltration or was indeterminate at baseline AND meets all the following criteria:
 
 
1) All nodal target lesions are normal.
 
2) All extranodal target lesions have resolved.
 
3) All nodal non-target lesions are normal.
 
4) All extranodal non-target lesions have resolved.
 
5) There is no enlarged liver, spleen, or kidney (all lesions have resolved).
 
6) There is no tumor-related symptom (fever and night sweat) (all symptom have resolved) OR no abnormal tumor-related laboratory test results (tumor-related increase in LDH) (normal).
 
7) The patient is indeterminate for bone marrow infiltration.
 
8) The patient has no new lesion.
 
 
OR
 
 
1) The patient has a 75% or more decrease (reduction) in the SPD of target lesion from baseline.
 
2) All nodal non-target lesions are normal.
 
3) All extranodal non-target lesions have resolved.
 
4) There is no enlarged liver, spleen, or kidney (all lesions have resolved).
 
5) There is no tumor-related symptom (fever and night sweat) (all symptom have resolved) OR no abnormal tumor-related laboratory test results (tumor-related increase in LDH) (normal).
 
6) The patient has no bone marrow infiltration or indeterminate.
 

	7) The patient has no new lesion.
PR	
The patient meets all the above criteria for CRu except for criterion 6. A patient with bone marrow infiltration or indeterminate at baseline must be positive for bone marrow infiltration at the time of restaging.
 
Or, the patient meets all the following criteria:
 
 
1) The patient has a 50% or more decrease (reduction) in the SPD of target lesion from baseline.
 
2) All nodal non-target lesions are normal or free from enlargement.
 
3) All extranodal non-target lesions have resolved or free from enlargement.
 
4) Enlarged liver, spleen, and kidneys have resolved or are free from progression.
 
5) All tumor-related symptom (fever and night sweat) have resolved. AND abnormal tumor-related laboratory test results (tumor-related increase in LDH) became normal.
 
6) Bone marrow infiltration does not matter. Testing is not required.
 
7) The patient has no new lesion.
 

SD	The patient achieved a response of <PR and >PD.
PD	
If the patient is not assessed as achieving CR or CRu but meets any of the criteria below, the patient will be assessed as having progressive disease (PD). If the patient meets any of the criteria listed below after being assessed as achieving CR or CRu, the patient will be assessed as having a relapsed disease (RD):
 
 
1) The patient has a 50% or more increase in the SPD of target lesion from the minimum SPD.
 
2) The patient has an obvious increase in the nodal non-target lesion (a 50% or more increase in the long diameter) or re-enlargement.
 
3) The patient has an obvious increase in the extranodal non-target lesion (a 50% or more increase in the long diameter) or recurrence.
 
4) The extranodal target lesion which once resolved and was assessed as CR or CRu reappeared.
 
5) Obvious progression or recurrence of enlarged liver, spleen, or kidney.
 
6) Obvious progression or recurrence of tumor-related subjective and objective symptoms (fever and night sweat) or abnormal tumor-related laboratory test results (tumor-related increase in LDH).
 
7) The patient became positive after being once negative for bone marrow infiltration.
 
8) The patient has a new lesion.
 

